## Table 6.1

### SOE footnotes

-  Belatacept dose 10 mg/kg IV administered at study day 0, week 2, month 1, 2, 3
-  Belatacept dose 5 mg/kg IV q month administered beginning study month 4 and continuing through end of study treatment period
-  Infusion dose based on subject's actual body weight at enrollment and will not be modified during the course of the study unless there is a change of body weight greater than  $\pm 10\%$
-  at first dose of belatacept, reduce CNI or mTOR inhibitor dose by 50%
-  at second dose of belatacept (week 2) discontinue CNI or mTOR inhibitor
-  Continue concomitant immunosuppression (MMF/MPA/AZA and/or prednisone) at current dose until initiation of dialysis
-  Decrease MMF/MPA/AZA dose by 50% at initiation of dialysis. Discontinue MMF/MPA/AZA 2 weeks after initiation of dialysis
-  Reduce prednisone dose by 50% one month after initiation of dialysis, by half again at 2 months after initiation of dialysis. Discontinue prednisone at 3 months after initiation of dialysis
-  After initiation of hemodialysis, infusion visits will be scheduled on non-dialysis days
-  Maintain target tacrolimus trough of 3-5 ng/ml (or equivalent CNI or mTOR inhibitor trough) until initiation of dialysis
-  Continue concomitant immunosuppression (MMF/MPA/AZA and/or prednisone) at current dose until initiation of dialysis
-  Discontinue CNI or mTOR inhibitor over 5 days after initiation of dialysis
-  Decrease MMF/MPA/AZA dose by 50% at initiation of dialysis. Discontinue MMF/MPA/AZA 2 weeks after initiation of dialysis
-  Reduce prednisone dose by 50% one month after initiation of dialysis, by 50% again at 2 months after initiation of dialysis. Discontinue prednisone at 3 months after initiation of dialysis

## 6.2 Screening Evaluation

Obtain written consent and enroll the subject. Consent will be obtained prior to any change in medical therapy or any procedure performed solely for the purpose of this study.

Review inclusion and exclusion criteria with patient; determine if they remain a candidate for the trial

Obtain a serum or urine pregnancy test

EBV serology done at any previous time point will be accepted for eligibility criteria and will be documented. If serology results are not available then serum will be sent for EBV antibody quantification. Both EBV and CMV viral titers will be checked prior to randomization. If the EBV viral load is positive in an EBV seropositive individual, the subject will have the EBV viral load repeated and the subject may be considered for enrollment when the result is undetectable. If CMV titer is positive, the subject will be appropriately treated and reconsidered for enrollment once the viral load is undetectable for >1 month period.

Obtain blood sample for donor specific antibody evaluation and overall allo-antibody levels. Donor specific antibody/anti-HLA antibody will be evaluated using the FlowPRA assay in the Emory University Hospital Clinical HLA Laboratory. The Emory Medical laboratory is a CLIA certified facility. If allo-antibody is detected then antigen specificity will be assessed using single-antigen HLA beads. Results from donor HLA typing will be used to determine if new anti-HLA antibody is donor specific constituting a new DSA.

Obtain a complete medical history and physical examination including a neurologic exam.

Obtain body weight (clothes on, shoes off) and height, measure vital signs (BP, HR, temp, respiration)

All women 50 years or older must have a screening mammogram, or provide results of a screening mammogram performed within the last year. Women of any age who have first degree relatives with a history of breast carcinoma or who have other risk factors of breast carcinoma must undergo increased surveillance for breast cancer according to local practice

Check and record all medications

Obtain baseline laboratory tests including serum Cr and related estimated GFR

### **6.3 Post-Enrollment/Randomization**

Prior to the first treatment time point, confirm all inclusion/exclusion criteria. Randomize when all entry criteria are satisfied. Randomization may take place prior to the first post-screening visit if required due to scheduling constraints.

Obtain vital signs, monitor for any adverse events, check and record any changes in medications immediately prior to first treatment session

For subsequent study assessments see respective charts for either belatacept-treated arm or standard of care group.

If during the course of immunosuppressive withdrawal, the kidney allograft becomes a source of symptoms (swelling, fever, local pain, and/or hematuria) or infection then trial participants will be treated according to standard of care as deemed appropriate by the treating physician including, if appropriate, a limited course of oral or intravenous corticosteroids or if required allograft nephrectomy. Study participants will remain on their treatment protocol (i.e. continue to receive belatacept or wean quickly off the corticosteroid treatment back to no immunosuppression in the standard of care arm). For the purposes of statistical analyses participants will be treated in an intent to treat fashion.

Study participants will have the option to consent for storage of a banked blood sample for future mechanistic assays. If the subject consents to blood for storage, an additional 10 ml sample of blood will be collected at enrollment and every 3 months during pre-dialysis period, upon initiation of dialysis, and every 3 months during post-initiation of dialysis period as noted on the schedule of events.

Banked samples will be stored in the PI's research lab. Samples may remain stored indefinitely. Subjects will have the ability request destruction of samples at any time.

## **6.4 Study Materials**

Bristol-Myers Squibb (BMS) will provide belatacept for this study.

## **6.5 Safety Assessments**

All subjects who are randomized and remain in the study will be evaluated for safety. Safety assessments include monitoring of adverse events, clinically significant changes in vital signs, physical examination, neurologic assessment, or laboratory test abnormalities. The investigator will determine the severity of each adverse event as mild, moderate, severe, or very severe. All adverse events will be documented. In addition the investigator will determine the relationship of the adverse event to the administration of belatacept.

All serious adverse events (SAEs) must be reported as described in Section 7.3.1. All nonserious adverse events must be collected as well and documented according to the procedures of the investigational site. They do not need to be sent to BMS.

If the patient is a WOCBP, pregnancy tests (blood or urine; minimum sensitivity 25 IU/L of HCG) must be performed within 72 hours before the first infusion. If the patient becomes pregnant at any point during the study, she will exit the study and belatacept treatment will be discontinued.

Laboratory tests may be performed as part of routine standard of care as directed by the investigator. Laboratory specimens should be obtained before belatacept infusions. Additional tests may be ordered if deemed necessary for monitoring the patient's safety.

### **PTLD Safety Surveillance**

Specific surveillance for PTLN will be conducted for all subjects in this study. The PTLN safety surveillance should be implemented as soon as IRB/IEC approvals and subject consent are obtained.

## Neurologic Examinations

To assess for PTLT, neurologic examinations will be conducted periodically for the duration of the subject's participation in the study. The neurologic history will include the subject's description of any new neurologic symptoms, such as:

- changes in personality
- changes in memory
- headaches
- pain
- seizures
- impairment of consciousness
- difficulty swallowing
- changes in vision, hearing, or language function
- changes in coordination or gait
- weakness
- sensory alterations
- sphincter disturbance, or
- involuntary movements.

In addition, the following will be recorded:

- time course of any new symptoms (onset and duration)
- corroboration of any complaints with other individuals
- medical illnesses, and
- medication use.

The neurologic examination will include assessment of:

- mental status
- gait
- speech
- cranial nerves
- cerebellar function
- sensory function
- motor function.

Any new or worsening findings should be reported as adverse events and evaluated with a follow up neurologic examination, additional modalities, and/or neurologic consultation as appropriate.

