| Safety Assessments                  |        |                |                |      |      |      |                  |      |       |      |       |      |                 |      |                 |      |        |      |        |      |
| Physician Visit                            | X      |                |                | X    | X    | X    |                  | X    |       | X    |       | X    |                 | X    |                 | X    |        | X    |        | X    |
| Physical Examination                       | X      |                |                | X    | X    | X    |                  | X    |       | X    |       | X    |                 | X    |                 | X    |        | X    |        | X    |
| Vital Signs                                | X      | X              | X              | X    | X    | X    | XX               | X    | XX    | X    | XX    | X    | XXXXXX          | X    | XXXXXX          | X    | XXXXXX | X    | XXXXXX | X    |
| Assessment of Signs and Symptoms           |        | X              | X              | X    | X    | X    | XX               | X    | XX    | X    | XX    | X    | XXXXXX          | X    | XXXXXX          | X    | XXXXXX | X    | XXXXXX | X    |
| Adverse Events Assessments                 |        | X              | X              | X    | X    | X    | XX               | X    | XX    | X    | XX    | X    | XXXXXX          | X    | XXXXXX          | X    | XXXXXX | X    | XXXXXX | X    |
| Laboratory Tests                           | X      | X              |                | X    | X    | X    |                  | X    |       | X    |       | X    |                 | X    |                 | X    |        | X    |        | X    |
| EBV/CMV titer                              | X      |                |                |      |      |      |                  |      |       |      |       |      |                 |      |                 |      |        |      |        |      |
| Neurologic Evaluation                      | X      |                |                | X    | X    | X    |                  | X    |       |      |       | X    |                 | X    |                 | X    |        | X    |        | X    |
| Efficacy Assessments                |        |                |                |      |      |      |                  |      |       |      |       |      |                 |      |                 |      |        |      |        |      |

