| Safety Assessments                   |        |          |          |          |          |          |          |          |          |          |          |          |
| Physician Visit                             | X      | X        | X        | X        | X        | X        | X        | X        | X        | X        | X        | X        |
| Physical Examination                        | X      |          | X        | X        | X        | X        | X        | X        | X        | X        | X        | X        |
| Vital Signs                                 | X      | X        | X        | X        | X        | X        | X        | X        | X        | X        | X        | X        |
| Assessment of Signs and Symptoms            |        | X        | X        | X        | X        | X        | X        | X        | X        | X        | X        | X        |
| Adverse Events Assessments                  |        | X        | X        | X        | X        | X        | X        | X        | X        | X        | X        | X        |
| Laboratory Tests                            | X      | X        | X        | X        | X        | X        | X        | X        | X        | X        | X        | X        |
| EBV/CMV titer                               | X      |          |          |          |          |          |          |          |          |          |          |          |
| Neurologic Evaluation                       | X      |          | X        |          | X        | X        |          | X        |          | X        |          | X        |
| Efficacy Assessments                 |        |          |          |          |          |          |          |          |          |          |          |          |
| DSA/PRA                                     | X      | X        | X        | X        | X        | X        | X        | X        | X        | X        | X        | X        |
| Mechanistic                                 |        |          |          |          |          |          |          |          |          |          |          |          |
| Sample storage                              | X      |          | X        | X        | X        | X        | X        | X        | X        | X        | X        | X        |
| Clinical Drug Supplies               |        |          |          |          |          |          |          |          |          |          |          |          |

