### 7.3 Collection and Reporting

Adverse events can be spontaneously reported or elicited during open-ended questioning, examination, or evaluation of a subject. To prevent reporting bias, subjects should not be questioned regarding the specific occurrence of one or more adverse events.

If known, the diagnosis of the underlying illness or disorder should be recorded, rather than its individual symptoms. The following information should be captured for all AEs: onset, duration, intensity, seriousness, relationship to investigational product, action taken, and treatment required. If treatment for the event was administered, it should be recorded in the medical record. The investigator must supply BMS and the IRB/IEC with any additional information requested, notably for reported deaths of subjects.

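### Before dialysis, Table 6.1 schedules nine neurologic evaluations on belatacept and six on control, so transient findings that become adverse events may look more frequent on belatacept

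*Combined protocol and SAP*

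**What the plan says.** Section 6.5, under PTLD Safety Surveillance, states that surveillance "will be conducted for all subjects in this study". Under Neurologic Examinations it sets out a history and an examination. The history part reads "The neurologic history will include the subject's description of any new neurologic symptoms, such as", followed by thirteen examples that include headaches, pain and weakness. After the list of examination components comes the rule "Any new or worsening findings should be reported as adverse events and evaluated with a follow up neurologic examination". The text of 6.5 gives no frequency beyond saying that examinations are periodic.

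The frequency is in the "Neurologic Evaluation" row of Table 6.1, which differs between the two pre-dialysis charts. Control has a physician visit, a physical examination, a signs-and-symptoms assessment and an adverse-event assessment at months 2, 18 and 30, but no neurologic evaluation.

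Section 7.3 gives the routes by which an adverse event may be recorded: "Adverse events can be spontaneously reported or elicited during open-ended questioning, examination, or evaluation of a subject". It then adds: "To prevent reporting bias, subjects should not be questioned regarding the specific occurrence of one or more adverse events".

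Section 8.3.2 summarizes adverse events by treatment group. It does not say whether events or subjects are counted, and makes no allowance for the number of evaluations.

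**The concern.** Each neurologic evaluation is an opportunity to record an adverse event. If one arm has more of these opportunities, part of any difference in recorded events reflects the schedule and not the drug. Here the arm examined more often is the experimental one, the assessors know the assignment, and the planned summary cannot separate the two sources.

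The outcome matters. Section 1.2.5.2 discusses CNS PTLD and PML at length, and 1.3.3 says that PTLD and CNS PTLD were seen more often on belatacept. Section 6.5 asks that imaging or consultation be considered for any new or worsening neurologic finding, so extra findings also lead to extra work-up. With 36 patients per arm, a few additional findings change the by-arm picture and make a true signal hard to tell from a scheduling artefact.

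No reason is given for the difference. Where 6.5 intends surveillance in one arm only, as with EBV titers in belatacept patients on dialysis, it says so. It says nothing of the kind for the neurologic examination.

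**Working it through.** **Inputs.** The Neurologic Evaluation row in each of the four Table 6.1 charts, matched to its time-point header. In the control pre-dialysis chart the first two time points print in one cell; I read them as day 0 (visit 2) and month 1 (visit 3). That reading affects the months assigned, not the count of six.

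| Chart | Evaluations after screening | Count |
|---|---|---|
| Belatacept, pre-dialysis | months 1, 2, 3, 6, 12, 18, 24, 30, 36 | 9 |
| Control, pre-dialysis | months 1, 3, 6, 12, 24, 36 | 6 |
| Belatacept, post-dialysis | initiation, months 3, 9, 12, 18, 24, 30, 36 | 8 |
| Control, post-dialysis | months 3, 6, 12, 18, 24, 30, 36 | 7 |

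**Growth of the gap before dialysis.** Cumulative evaluations, belatacept v control: 4 v 3 by month 6, 5 v 4 by month 12, 6 v 4 by month 18, 7 v 5 by month 24, 8 v 5 by month 30, 9 v 6 by month 36.

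**Range of the ratio, with equal true risk.** If findings persist or are recalled at the next evaluation, both arms record them and the ratio is about 1.0. If findings are transient, independent between evaluations and seen only at the evaluation, expected findings are proportional to the number of evaluations: 9/6 = 1.5.

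**Subjects with at least one finding, transient case.** The formula is P = 1 − (1 − q)^k, where k is the number of evaluations and q the chance of a finding at each. The documents give no q; I assume 1% to 10%.

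| q | Pre-dialysis to month 36, k = 9 v 6 | Pre-dialysis to month 12, k = 5 v 4 | Post-dialysis, k = 8 v 7 |
|---|---|---|---|
| 1% | 8.6% v 5.9% | 4.9% v 3.9% | 7.7% v 6.8% |
| 2% | 16.6% v 11.4% | 9.6% v 7.8% | 14.9% v 13.2% |
| 5% | 37.0% v 26.5% | 22.6% v 18.5% | 33.7% v 30.2% |
| 10% | 61.3% v 46.9% | 41.0% v 34.4% | 57.0% v 52.2% |

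The excess at month 36 runs from about 3 points (q = 1%) to 14 points (q = 10%). It has a ceiling for any q. With x = (1 − q)^3 the excess is x² − x³, which is largest at x = 2/3 and equals 4/9 − 8/27 = 4/27, or 14.8 points.

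**Context.** The "Adverse Events Assessments" row before dialysis has 38 entries on belatacept (day 0, week 2 and months 1 to 36: 1 + 1 + 36) and 11 on control (day 0 and months 1, 2, 3, 6, 9, 12, 18, 24, 30, 36).

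**The case against.** The strongest reply is that the schedule gap rarely reaches the record. Control patients have signs-and-symptoms and adverse-event assessments at every visit from day 0, including months 2, 18 and 30, so a new headache or weakness has a route to the record there too. Both arms have a neurologic evaluation at months 3, 24 and 36, the scheduled visits that follow the three omissions, so anything that persists is caught. The full 9 v 6 gap needs 36 months off dialysis in patients enrolled with failing grafts, some already on dialysis. The safety summary is descriptive, with no neurologic endpoint or test, and confirmed PTLD is reported separately. All of this stands. It limits the effect to transient findings detectable only at the neurologic evaluation.

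Three stronger readings are tempting, and the documents support none of them.

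- A reader might infer that neurologic events will look more frequent on belatacept. The ratio can be 1.0, so the most that can be said is that they may.
- A reader might infer that every new symptom becomes an adverse event. The rule speaks of findings and follows the examination list. Symptoms may be meant, but this is not stated.
- A reader might infer that 6.5 breaks the no-prompting rule in 7.3. Section 7.3 allows events elicited by examination or evaluation, and 6.5 asks for the subject's own description with examples; it does not prescribe a checklist to be read out. This is an ambiguity, not a flat contradiction.

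**Conclusion.** The imbalance is in the schedule and is unexplained: nine evaluations against six before dialysis, under a surveillance plan described as applying to everyone, at visits that control patients already attend. The planned summary does not account for it.

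The effect is possible ascertainment bias against belatacept, with a scheduling ratio between 1.0 and 1.5. The excess of about 3 to 14 points is an upper-end illustration. It assumes equal true risk, a 1% to 10% chance per evaluation, transient and independent findings recorded only at that evaluation, and 36 months off dialysis. For patients who reach dialysis sooner the pre-dialysis gap is smaller, and the post-dialysis schedules are nearly equal. The concern does not extend to confirmed PTLD, nor to symptoms that patients would report at any visit.

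**What to change.** 1. Reconcile the two pre-dialysis Neurologic Evaluation rows in Table 6.1 so that both arms follow the same months. Which months is for the sponsor.
2. In 8.3.2, flag findings elicited by the neurologic evaluation and tabulate them apart from events reported in other ways.
3. In 6.5, state whether symptoms from the neurologic history count as findings, and make this consistent with 7.3.
4. If the rows stay unequal, compare the arms at the shared months (1, 3, 6, 12, 24, 36). In both arms, count any finding present at that evaluation and new since the previous shared evaluation, even if belatacept first recorded it at an interim month. List all other findings.

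The wording in item 4 matters. Simply dropping belatacept findings from months 2, 18 and 30 would reverse the bias. A belatacept finding first seen at month 18 would no longer be new at month 24 and would drop out, while the same finding arising in control after month 12 would first be seen at month 24 and be counted.

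The cost is one schedule correction, a few sentences and a source flag on each event. Aligning the rows needs no new visit for control if the months chosen are ones it already attends. Under item 4, transient belatacept findings seen only at unshared months are listed but not compared. None of this removes the larger imbalance in general adverse-event assessments (38 v 11 before dialysis), which needs its own remedy.

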### **EBV Titers**

Subjects receiving belatacept who are on dialysis will have samples sent for EBV viral titers periodically for the duration of the study. Positive titers will be confirmed and subjects will exit the study and belatacept treatment will be discontinued if they have persistent positive titers. Again only patients who are seropositive for EBV will be enrolled in the study.

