End stage renal disease is a major health problem affecting over 350,000 people in the US alone. Kidney transplantation is now the ideal treatment for renal failure, with nearly 17,000 transplants performed annually. While early outcomes have improved dramatically over the past 30 years, long-term results continue to be disappointing. Ten years after transplant nearly all renal allografts have histologic evidence of chronic injury with accompanying impaired renal function. Many patients with failing allografts ultimately return to dialysis. Fortunately, a significant proportion of these patients are re-transplant candidates. Indeed 10-15% of all renal transplants are performed in recipients of prior renal allografts. There is an ongoing debate regarding the management of patients with a failed kidney transplant. Those patients who require dialysis and are maintained on immunosuppression continue to be subjected to increased risks of infection, cardiovascular disease, malignancies, etc. In fact several studies have shown a significantly increased risk of infection and death for those who continue immunosuppression after graft failure. Thus most centers favor tapering immunosuppressive therapy off once a patient requires dialysis. Unfortunately, this puts the patient at risk for developing allo-antibody which may limit options for re-transplant. The development of an immunosuppressive strategy to minimize the complications of persistent therapy while preventing sensitization could greatly enhance the likelihood of re-transplantation.

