**4.2.3 Discontinuation of Subjects from Treatment**

Subjects MUST discontinue study treatment and withdraw from the study for any of the following reasons:

- Withdrawal of informed consent (subject’s decision to withdraw for any reason)
- Any clinical adverse event (AE), laboratory abnormality, or intercurrent illness which, in the opinion of the investigator, indicates that continued participation in the study is not in the best interest of the subject
- Pregnancy
  - Instruct WOCBP to contact the investigator or study staff immediately if they suspect they might be pregnant (eg, missed or late menstrual period) at any time during study participation. Institutional policy and local regulations should determine the frequency of on-study pregnancy tests for WOCBP enrolled in the study.
  - The investigator must immediately notify BMS if a study subject becomes pregnant. The mechanism for reporting pregnancy is described in Section 7.6.
- Termination of the study by BMS.
- Loss of ability to freely provide consent through imprisonment or involuntarily incarceration for treatment of either a psychiatric or physical (eg, infectious disease) illness.

Subjects who discontinue from the study for any reason other than withdrawal of consent will be asked to continue in the study under a reduced follow-up plan.

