#### **5.4.1 Dose Modifications**

In the absence of AEs deemed at least possibly related to study drug treatment, subjects will complete their scheduled infusions as prescribed by the protocol. In the event of new, serious, and unexpected toxicity potentially related to belatacept, study drug administration should be interrupted. The investigator must immediately notify the medical monitor. The subject will be considered eligible to receive further study drug treatment only after discussion with the medical monitor. Under no circumstances should the dose of belatacept be modified. Subjects in whom belatacept dosing is discontinued should be placed on the standard of care regimen.

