## **6 STUDY ASSESSMENTS AND PROCEDURES**

### **6.1 Time and Events Schedule**

Baseline and study evaluations are summarized in table 6.1

All assessments will be performed or administered prior to study drug administration unless otherwise indicated.

If a subject needs to withdraw from the study, the next scheduled set of assessments will be performed early. The reason for study discontinuation will be documented.

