## **7.7 Other Safety Considerations**

Any significant worsening noted during interim or final physical examinations, electrocardiograms, x-rays, and any other potential safety assessments, whether or not these procedures are required by the protocol, should also be recorded in the medical record.

Subjects who prematurely withdraw or are terminated from study participation, for reasons other than withdrawal if consent, will be asked to continue in a reduced safety follow-up schedule. The study team will contact the patient every 3 months for the duration of the trial to assess patient survival, dialysis status, and serious adverse event occurrences.

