### 8.3.3 Efficacy Analyses

There will be two main methods of analyzing the primary outcome at the study end. One will be a chi-squared test comparing the proportion of patients who developed donor specific antibodies in each study group. The second analysis will be a log-rank test comparing the Kaplan-Meier time to event curves between the two study groups. In both cases we will use a two-sided test with a significance level of 0.05.

The sample size for each arm will be 36 patients. This sample size calculation is based on several assumptions. We assume that the incidence of developing donor-specific antibody among the control group is 60% and among the belatacept-treated group it is 20% or less. We also assume an alpha level of 0.05 and corresponding  $Z\text{-alpha} = 1.96$  and a one-to-one ration of exposed to unexposed subjects. Calculations with these estimates yield a power of 90% to detect a three-fold difference in risk of developing donor specific antibodies between the control and belatacept-treated group.

In addition to the aforementioned assumptions, additional assumptions required for the log-rank test include no loss to follow-up in 36 months and that the distribution of the incidence of the primary endpoint follows an exponential distribution. Assuming an incidence of development of anti-donor antibody in the control group is 60% at 36 months then the hazard rate can be calculated as 0.02545. In the treatment arm, if the incidence of the primary endpoint is 30% then the hazard ratio becomes 0.0099 and if the incidence is 20% then the hazard rate is 0.00619.

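### The EBV rule for belatacept subjects on dialysis ends study participation as well as the drug, so their later donor-specific antibody goes unmeasured in one arm only

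*Combined protocol and SAP*

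**What the plan says.** The EBV Titers paragraph of section 6.5 provides periodic viral titres for belatacept subjects who are on dialysis, and then states: "Positive titers will be confirmed and subjects will exit the study and belatacept treatment will be discontinued if they have persistent positive titers". The consequence is therefore twofold: the drug stops and the subject leaves the study.

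Three places describe what happens after that:

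- Section 6.1: when a subject withdraws, "the next scheduled set of assessments will be performed early".
- Section 4.2.3: subjects who discontinue for any reason other than withdrawn consent "will be asked to continue in the study under a reduced follow-up plan".
- Section 7.7: that plan is a contact every 3 months "to assess patient survival, dialysis status, and serious adverse event occurrences". DSA is not on the list.

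Table 6.1 schedules repeated EBV/CMV titres in the belatacept post-dialysis chart. In the standard of care post-dialysis chart the EBV/CMV row is empty, while DSA/PRA is scheduled through month 36.

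The primary endpoint (sections 2.1 and 8.2) is DSA formation 36 months after randomization. Section 6.3 adds: "For the purposes of statistical analyses participants will be treated in an intent to treat fashion". Section 8 does not say how a subject who left before month 36 enters the chi-squared proportion.

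**The concern.** Stopping belatacept protects a subject with persistent viraemia. Leaving the study adds no protection and closes observation of the primary endpoint. DSA found before exit still counts, but DSA that forms afterwards is never seen.

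The loss is unlikely to be neutral. By the plan, a belatacept subject on dialysis has already lost the CNI or mTOR inhibitor, or is about to lose it. The antimetabolite stops 2 weeks after dialysis begins and the steroid at 3 months. Once belatacept stops, little or no immunosuppression remains. Of tapering off at dialysis, section 1.3.3 says "this puts the patient at risk for developing allo-antibody which may limit options for re-transplant". Observation therefore ends as the risk of the outcome rises.

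The EBV rule also works in one arm only. Withdrawals for adverse events or pregnancy under section 4.2.3 lose DSA as well, but they can occur in either arm. In an open-label comparison with 36 per arm, or 18 if Phase II is not funded, a one-sided loss of outcome data tends to favour belatacept.

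**Working it through.** **1. The plan's own figures.** Section 8.3.3 assumes 60% DSA in control and 20% on belatacept at 36 months, exponential times, 36 per arm and two-sided alpha 0.05.

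- Control hazard: −ln(0.40)/36 = 0.02545 per month, as stated.
- Belatacept hazard: −ln(0.80)/36 = 0.00620 (the plan prints 0.00619).
- Power: 91.7% with a continuity-corrected normal approximation and 91.3% with Fisher's exact test, in line with the stated 90%. The uncorrected chi-square, evaluated exactly, gives 94.9%. The plan mentions no correction, so this version is used below.

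**2. Draws lost.** As the belatacept post-dialysis chart reads, DSA/PRA falls at months 2, 3, 4, 5, 6, 12, 24, 30 and 36 after dialysis begins. For a subject on dialysis from enrollment:

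- Exit after the month 1 titre loses 9 draws less the month 2 set brought forward, so 8.
- Exit after month 6 loses 4, and after month 12 loses 3.

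The visits after the month 6, 12, 18, 24 and 30 titres show no DSA/PRA, so the one early set may or may not contain it. The chart's columns are irregular in the available text, so these counts are approximate.

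**3. Chance of later, unobserved DSA.** For a subject still DSA-free who exits at study month t, the chance by month 36 is 1 − exp(−h(36 − t)).

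| Exit month | Control hazard after the stop | Belatacept hazard after the stop |
|---|---|---|
| 1 | 59% | 19% |
| 6 | 53% | 17% |
| 12 | 46% | 14% |
| 24 | 26% | 7% |

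**4. Understatement of the belatacept rate.** The documents give no exit rate, so k = 1 to 4 of 36 is an assumption. Apply the belatacept hazard before exit and the control hazard after it. If exits count as DSA-free, the understatement is (k/36) × exp(−0.00620t) × [1 − exp(−0.02545(36 − t))].

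| Exit month | Per exit | 4 exits |
|---|---|---|
| 6 | 0.9635 × 0.5340 / 36 = 1.4 points | 5.7 points |
| 12 | 0.9283 × 0.4571 / 36 = 1.2 points | 4.7 points |
| 24 | 0.8618 × 0.2632 / 36 = 0.6 points | 2.5 points |

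If exits are censored, the estimate stays at 20.0%. The intent-to-treat rate is 21.0% to 23.9% for exits at month 6 and 20.8% to 23.3% at month 12, an understatement of 0.8 to 3.9 points. With 18 per arm and 1 or 2 exits at months 6 to 12, the figures are 2.4 to 5.7 points (DSA-free) and 1.6 to 3.9 points (censored).

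If risk after the stop stayed at the belatacept hazard, one exit at month 6 counted DSA-free would cost only 0.9635 × 0.170 / 36 = 0.5 points, and censoring would cause no bias.

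**5. False positives favouring belatacept.** Take 60% in both arms and 36 per arm. With exits coded DSA-free in the chi-square, the chance rises from 2.5% with no exits to 3.1%, 3.8%, 4.7% and 5.7% for 1 to 4 exits at month 6. At month 24 it is 2.7% to 3.3%. If exits are censored in the log-rank test there is no inflation: simulation gives 2.6% with no exits and 2.5% with 4 at month 6.

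**6. Power if DSA is followed after the stop.** For stops at month 6 with 36 per arm, 94.9% becomes 93.7%, 92.4%, 90.8% and 89.0% for 1 to 4 stops. With 18 per arm, 74.2% becomes 69.8% (1) and 65.0% (2).

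**The case against.** The strongest reply is that the rule is narrow and its effect unknown. It applies only on dialysis, only to a confirmed and persistent titre, and only in subjects whose EBV load had to be undetectable at entry. Exit at study months 6 to 12 requires dialysis at or soon after enrollment, and section 8.3.3 calls those already on dialysis at entry a small subset. Four exits of 36 has no support in the documents. All of this stands, and it is why the month 24 figures belong beside the earlier ones.

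A reader might infer more than the documents support:

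- *That all belatacept subjects face this rule.* The paragraph covers those on dialysis only.
- *That the trial's type I error is inflated.* That needs exits coded DSA-free in the chi-square. No section prescribes this coding, and the log-rank, the other main analysis, is not inflated by censoring when there is no treatment effect.
- *That the exit rule contradicts other sections.* Section 5.4.1 says "Subjects in whom belatacept dosing is discontinued should be placed on the standard of care regimen", which settles the regimen and not retention. The assumption of "no loss to follow-up in 36 months" belongs to the log-rank sample-size reasoning and is not a conduct rule. Intent-to-treat analysis is strained by missing outcomes, but it does not forbid exit. These are tensions.
- *That EBV titres should be added before dialysis.* The documents show no benefit from this, and section 1.3.3 reports no increase in PTLD risk in EBV-positive recipients.

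Two further points are fair. The early assessment set could be read as the next full set, including DSA, but that still leaves nothing up to month 36. Section 4.2.3 also forces withdrawal for a laboratory abnormality that the investigator judges sufficient, so editing section 6.5 alone would leave another route to the same loss.

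**Conclusion.** The point holds in a limited form. Followed as written, the plan stops collecting the primary endpoint for belatacept subjects on dialysis who have persistent EBV titres. The EBV rule has no counterpart in the control arm, and the loss comes when sensitization is more likely. The text supports this with high confidence.

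The size is uncertain and probably modest. The ranges in the working rest on an assumed 1 to 4 exits of 36 and on control-level risk after belatacept stops. Against a planned 40-point difference, such a bias would matter only if exits were several and early, or if the trial ended at 18 per arm. The direction favours belatacept, and the main harm is bias rather than lost power. A change is worth making because it is cheap, not because the trial's conclusion is likely to turn on it.

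**What to change.** In section 6.5, replace the study exit with this instruction: discontinue belatacept, remain in the study, and continue DSA/PRA at the Table 6.1 visits through month 36, analysed by intent to treat. State that replacement immunosuppression is decided with the BMS medical monitor, the route section 6.5 already uses for suspected PTLD.

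Make the matching change in sections 4.2.3 and 7.7, so that subjects in either arm who stop treatment without withdrawing consent keep DSA/PRA sampling in their follow-up.

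Costs: up to about 8 further scheduled draws per affected subject (8 to 32 for an assumed 1 to 4 EBV stops), continued attendance by people no longer receiving study drug, and the modest loss of power in step 6 of the working. That loss reflects antibody which the present rule would leave unseen.
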